### **Intervention**

The patients were randomized into an exercise (n=25) and a control (n=25) group. Both groups were informed about systemic sclerosis and they received the printed materials that include recommendations such as avoiding cold and trauma. The treatment group participated in a single hand exercise training (isometric hand exercise and self-administered stretching) applied by a physiatrist. Isometric exercise was told as the ball squeeze exercise. Accordingly, patients squeezed the soft small ball for 60 seconds. This repeated 15 times in each set. Three sets were recommended per day. The stretching exercises were as follows; i) forearm supination and pronation, ii) wrist flexion and extension, iii) finger flexion, extension and abduction iv) thumb flexion, extension and abduction. Holding each stretch was recommended for 30 seconds. Thereafter, patients took instructions illustrating the exercises. The 8-week intervention consisted of isometric hand exercise 15-times/3

set and self-administered stretching repeated 10-times/2 set per day. Compliance was assessed by a checklist, which included all information on how to exercise and how many times to do them.

### **Statistical analysis**

Statistical analysis was performed by IBM SPSS version 20.0 (SPSS Inc., Chicago, IL, USA). Descriptive statistics was used to analyze the demographic and clinical variables. The normality of the variables was checked by Shapiro-Wilk test. Non-parametric values were given as median and interquartile range. Between-group comparisons of continuous and categorical variables were performed by Mann-Whitney *U* test and Chi-square test, respectively. Within-group comparisons over time analyzed by Friedman test. Delta ( $\Delta$ ) values were calculated as the difference from baseline measurement to the second visit measurement.  $\Delta$  values were compared between groups by Mann-Whitney *U* test. In addition, apart from  $\Delta$  values, the percentages of improvement or worsening on grip strength, DHI, HAMIS, HAQ-DI, Beck Depression and Beck Anxiety were calculated according to the formula as  $[(\text{Last assessment} - \text{Baseline assessment}) / \text{Baseline assessment}] \times 100$ . Multiple Linear regression analysis was used to define the predictors impacting on the percentages of improvement or worsening of HAMIS, DHI, handgrip strength, and HAQ-DI. The results were considered as statistically significant when *p* values below 0.05.

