### **Sample size**

Handgrip strength was determined as the primary outcome measure. According to the literature, handgrip strength has been reported to have a standard deviation between 6 and 7 [35]. Accordingly, standard deviation as 7 and autocorrelation coefficient as 0.3 were accepted in the current study evaluating the average of three consecutive measurements of handgrip strength. The sample size was calculated as 24 participants for each group in order to detect at least 4 kg differences with a 95% confidence interval and 80% power.

DHI was defined as the secondary outcome measure. We calculated the mean standard deviation as the mean of the total DHI for two time-points and two groups  $(20.20+16.22+17.1+17.85)/4=17.5$  [23]. We expected at least 5-6 points regression in the control group and at least >5-6 points improvement in the treatment group, so that, we assumed that there could be at least 12 points differences between groups. The number of observations, to find this difference significant at alpha=0.05 with 80% power, was calculated to be at least 23 per group.

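### Change from baseline is compared by an unadjusted Mann-Whitney test, with no baseline-adjusted comparison and no kg estimate with a CI to set against the 4 kg target

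*Combined protocol and SAP*

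**What the plan says.** The Sample size section sets the primary outcome: "Handgrip strength was determined as the primary outcome measure". It takes "standard deviation as 7 and autocorrelation coefficient as 0.3 were accepted" for a study "evaluating the average of three consecutive measurements of handgrip strength", and arrives at 24 per group "in order to detect at least 4 kg differences with a 95% confidence interval and 80% power". For the Duruoz Hand Index (DHI), the secondary outcome, "we assumed that there could be at least 12 points differences between groups".

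In the Statistical analysis section, delta "values were calculated as the difference from baseline measurement to the second visit measurement", and these "values were compared between groups by Mann-Whitney" U test. The same test is listed for between-group comparisons of continuous variables in general. Percentage change is calculated as well. None of these is named as the primary handgrip analysis.

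Summaries are medians with interquartile ranges. A 95% confidence interval is mentioned only in the sample-size statement. The one model is exploratory: "Multiple Linear regression analysis was used to define the predictors impacting on the percentages of improvement or worsening" of HAMIS, DHI, handgrip and HAQ-DI. Its predictors are not listed.

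**The concern.** Subtracting baseline fixes its slope at 1. If the two visits have equal SDs and correlation r, the best linear slope is r, so a full subtraction carries surplus baseline noise into the comparison. Below r = 0.5 the change score varies more than the follow-up value alone. ANCOVA estimates the slope from the data.

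The second gap does not depend on r. A Mann-Whitney p-value with medians and quartiles gives no between-group difference in kg and no interval. The trial was sized on 4 kg, yet it could finish without a result that shows whether 4 kg is supported or excluded.

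The regression does not fill either gap. Its outcome is percentage change, which has baseline in its denominator and is not in kg, and it is not described as the treatment comparison.

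**Working it through.** **Inputs.** From Sample size: SD 7 kg, autocorrelation 0.3, mean of three readings, 4 kg, 80% power, 24 per group; for DHI, SD 17.5 and 12 points. From Intervention: 25 per arm. Assumed: two-sided 0.05, equal SDs at both visits, and r from 0.3 to 0.9. The plan's 0.3 is attached to three consecutive measurements and is not stated to be the baseline-to-follow-up correlation.

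**1. The plan's own figure.** If 0.3 is an AR(1) correlation among three readings, the SD of their mean is 7 × √[(3 + 2(2 × 0.3 + 0.09))/9] = 4.88 kg. Then n = 2 × (1.96 + 0.84)² × 4.88²/4² ≈ 23.4, rounded up to 24, as stated. A compound-symmetry reading gives SD 5.11 and n = 26. An unreduced SD of 7 gives n = 49. The calculation that yields 24 compares means and subtracts no baseline.

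**2. Variances.** Change score: 2(1 − r)SD². ANCOVA: (1 − r²)SD². Their ratio is 2/(1 + r): 1.54, 1.33, 1.18 and 1.05 at r = 0.3, 0.5, 0.7 and 0.9. The change score has the variance used for the 24 only at r = 0.5. With SD 4.88, n per group for 80% power (change score against ANCOVA, normal theory) is 33 against 22 at r = 0.3, 24 against 18 at 0.5, and 15 against 12 at 0.7.

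**3. Power.** 10,000 simulated trials per cell, normal data, 25 per arm. Each cell shows Mann-Whitney on delta / ANCOVA.

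| r | 4 kg, SD 4.88 | 4 kg, SD 7 | DHI 12 points, SD 17.5 |
|---|---|---|---|
| 0.3 | 65% / 84% | 36% / 54% | 48% / 69% |
| 0.5 | 78% / 90% | 48% / 62% | 63% / 77% |
| 0.7 | 95% / 98% | 70% / 79% | 84% / 91% |
| 0.9 | 100% / 100% | 99% / 99% | 100% / 100% |

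Type I error was 0.047 / 0.052 at r = 0.3 and 0.049 / 0.052 at r = 0.7.

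**4. Expected 95% CI half-width.** t × √variance × √(2/25), with 48 df for the mean change and 47 for ANCOVA. Each cell shows mean change / ANCOVA.

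| r | SD 4.88 | SD 7 |
|---|---|---|
| 0.3 | 3.29 / 2.65 kg | 4.71 / 3.80 kg |
| 0.5 | 2.78 / 2.41 kg | 3.98 / 3.45 kg |
| 0.7 | 2.15 / 1.98 kg | 3.08 / 2.84 kg |
| 0.9 | 1.24 / 1.21 kg | 1.78 / 1.74 kg |

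**5. Chance imbalance.** Given a baseline difference of one standard error, SD × √(2/25), the change-score estimate shifts by (1 − r) times that amount. At SD 7 this is 0.7 × 7 × 0.283 = 1.39 kg (r = 0.3), falling to 0.20 kg (r = 0.9). At SD 4.88 it is 0.97 kg, falling to 0.14 kg. Over all randomizations these shifts average to zero.

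**6. Heavy tails.** Normal subject effect with t₃ occasion errors, SD 7. Mann-Whitney on delta / ANCOVA / rank ANCOVA (Quade): 53/61/69% at r = 0.3, 67/68/73% at 0.5, and 87/82/84% at 0.7. The ranking of the first two reverses at high r.

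HAMIS, HAQ-DI, SF-36, BDI and BAI were not computed, because the documents give no SD or target for them.

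**The case against.** The strongest reply is that nothing here is an error. A rank test on change from baseline is recognised, it uses baseline, and it holds its type I error. The loss depends on an r that the documents do not give. At the SD that reproduces the plan's 24, the planned test has about 80% power from r of about 0.5, and at r = 0.7 it gives up only 3 points from 98%. For DHI, the 12 points add worsening in controls to improvement under treatment, which is a contrast of changes. A change score with r of about 0.67 would give the stated 23 per group, although the plan does not say so, and near that r the power is about 80% against 88%. Normality is assumed in the main figures. The interval gap could be closed without ANCOVA by a Hodges-Lehmann shift with a CI. The regression's predictors are unlisted, so baseline could be among them.

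Much of this stands as a limit on size: the power loss matters most at low to moderate r and is negligible near 0.9. It does not supply the missing treatment comparison, primary analysis or interval. A Hodges-Lehmann interval would answer the reporting gap but recover no precision.

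Three practical points also stand. A rank-based option chosen after looking at the data needs a rule fixed beforehand. The plan speaks of both a second visit and a last assessment, and Friedman's test suggests more than two time points, so the analysis time point must be stated. The text is in the past tense, so a model added now may be post hoc.

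**Conclusion.** The concern holds. The plan has no baseline-adjusted treatment comparison, no named primary analysis for handgrip, and no between-group estimate with an interval to hold against 4 kg. The last two gaps do not depend on r.

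The precision loss does. At SD 4.88 with normal data it is about 19 power points at r = 0.3, 12 at 0.5, 3 at 0.7 and none at 0.9. At r = 0.3 the planned test falls below the intended 80% while ANCOVA does not. At SD 7 neither method reaches 80% up to r = 0.7. These figures rest on equal variances, a linear baseline relation and an assumed r. With heavy tails and high r the planned test can do better. Validity is not in question, so this is a change that should be made rather than a flaw that invalidates the result.

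**What to change.** Name one primary analysis: ANCOVA of handgrip strength at the end of the 8-week intervention on treatment group, with baseline handgrip as covariate, reporting the adjusted difference in kg with a 95% CI. State which visit supplies the follow-up value.

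Use the same baseline-adjusted approach for DHI, HAMIS, HAQ-DI, SF-36, BDI and BAI, with rank-based ANCOVA where a score is clearly non-normal, and write down beforehand the rule for choosing it. Keep Mann-Whitney on delta as a stated sensitivity analysis; a Hodges-Lehmann shift with its CI could accompany it.

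The cost is analysis wording. Baseline values are already collected, linear regression is already in the plan, and no visits or patients are added. The price is a linear-model assumption and some power if errors are heavy-tailed and r is high (82% against 87% at r = 0.7 in the t₃ simulation). If outcome data have already been examined, label the adjusted analysis as added later.

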**Evaluation of Patients**

The demographic variables and socio-economic status of patients were recorded at the beginning of the study. The time from the beginning of non-Raynaud's phenomenon symptoms was regarded as disease duration. The systemic sclerosis subsets including limited systemic sclerosis and diffuse systemic sclerosis were classified according to the definition of LeRoy et al. The organ involvements including interstitial lung disease, pulmonary arterial hypertension, scleroderma renal crisis, and gastroesophageal reflux disease were recorded based on the medical data. The present or absent of clinical variables such as Raynaud's phenomenon, digital pitting scars, arthralgia, sclerodactyly, calcinosis, color change, and telangiectasias was noted as well. Patients were questioned about cigarette smoking (package/years), medical drug information (previous and current) and comorbidities causing hand dysfunction (diabetes mellitus, atherosclerosis, thyroid diseases). Additionally, the laboratory results including anti-nuclear antibody, anti-Scl 70 antibody, anti-centromer antibody, complement levels (C3 and C4), erythrocyte sedimentation rate (ESR) (mm/h), and C-reactive protein (CRP) (mg/dl) were recorded.

The evaluation of disease activity and severity was performed by Valentini disease activity index and Medsger disease severity scale. Modified Rodnan Skin Score was used to assess the severity and the extent of

skin involvement. Hand involvement of patients was exhaustively evaluated by means of physical examination and indexes assessing the hand function. The finger range of motion was performed by the measure of finger-to-palm. The functional disability of hand was examined by Hand mobility in Scleroderma (HAMIS) test. Hand function was also evaluated by Duruoz Hand Index (DHI). Handgrip strength was measured by hydraulic hand dynamometer (JAMAR®, USA) according to the standard protocol. The physical function and quality of life were assessed by using Health Assessment Questionnaire-Disability Index (HAQ-DI) and Short-Form 36 (SF-36). Psychological status was evaluated by using Beck Depression Inventory (BDI) and Beck Anxiety Inventory (BAI).

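### The four predictor regressions use percentage change from baseline as the outcome, which is undefined at a zero baseline, can flag mere markers of baseline, and usually costs precision when error does not grow with baseline

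*Combined protocol and SAP*

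**What the plan says.** The Statistical analysis section defines a percentage for six measures: "the percentages of improvement or worsening on grip strength, DHI, HAMIS, HAQ-DI, Beck Depression and Beck Anxiety were calculated according to the formula", namely last minus baseline, divided by baseline, times 100. For four of them this percentage is the regression outcome: "Multiple Linear regression analysis was used to define the predictors impacting on the percentages of improvement or worsening of HAMIS, DHI, handgrip strength", with HAQ-DI as the fourth. The section lists no candidate predictors, does not say whether the baseline score or the randomised arm is a regressor, and gives no rule for a baseline of zero.

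The between-group comparison is separate. It applies the Mann-Whitney U test to delta, the "difference from baseline measurement to the second visit measurement", so it works on the absolute scale. The percentage formula refers to the last assessment instead, and the plan does not say that the two visits are the same.

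The Sample size section also sets its targets on the absolute scale: for grip, "in order to detect at least 4 kg differences"; for DHI, "we assumed that there could be at least 12 points differences between groups".

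**The concern.** There are three separate difficulties.

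1. A patient with a baseline of zero has no percentage and drops out of that regression. A patient just above zero can dominate it.
2. A baseline score that is high by chance both shrinks the numerator and enlarges the denominator. Anything correlated with the observed baseline can then appear to predict improvement. The Evaluation of Patients section collects several plausible candidates ("The evaluation of disease activity and severity was performed by" two named indices, plus a skin score).
3. If arm is a regressor, dividing by a noisy baseline can add variance and reduce power.

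At stake is what the report says about who improves. Such statements could reflect who started better or worse, or who had a small denominator.

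**Working it through.** **The plan's own figure.** No figure is attached to the regressions. The nearest is the grip sample size of 24 per group (SD 7, autocorrelation 0.3, mean of three readings, 4 kg, 80% power). The SD of the mean of three is 7 × √((1 + 2 × 0.3)/3) = 5.11. Then n = 2 × (5.11 × (1.96 + 0.84)/4)² ≈ 25.6, so 26 against 24. This is close, and it is not in dispute here. SD 7 and 4 kg are carried forward.

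**Scale.** A 4 kg gain is 4/15 = 26.7% from an assumed baseline of 15 kg and 4/25 = 16.0% from 25 kg. A 6-point DHI worsening is 6/20 = 30% from 20 points, 6/2 = 300% from 2 points, and undefined from 0.

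**Zero baselines.** With 50 patients, the chance of at least one zero is 1 − (1 − p)^50. The documents do not give p, so a range is assumed:

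| Assumed p | Chance of at least one | Expected number lost |
|---|---|---|
| 2% | 64% | 1 |
| 5% | 92% | 2.5 |
| 10% | 99% | 5 |

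**Simulation set-ups for grip** (25 per arm, SD 7, +4 kg, least squares, two-sided 5%). The following are assumptions, not taken from the documents.
- Set-up A: true status plus independent error at each visit; baseline means 15 to 25 kg; baseline-to-follow-up correlation 0.6 or 0.8.
- Set-up B: follow-up regressed on baseline with slope 1, 0.7 or 0.5 (correlation 0.7, 0.7, 0.5); means 18 or 24 kg; marker correlated 0.5 with baseline.

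**Inert marker of the observed baseline, share flagged.**
- Set-up A: 24-67% with percentage change and no baseline term; 4-7% with follow-up adjusted for baseline.
- Set-up B: 21-60% at slopes 0.5-0.7, but only 5-9% at slope 1; 4-6% with follow-up adjusted for baseline. Adding baseline to the percentage model also gives about 4-6%. Absolute change without baseline gives 12-42% at slopes 0.5-0.7.

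**Inert marker of true status** (set-up A). The order reverses: 4-20% with percentage change, 30-52% with follow-up adjusted for baseline. In a similar grid, absolute change gave 4-6% for this marker, but 17-60% for a marker of the observed baseline.

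**Power for arm, if arm is a regressor.**

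| Set-up | Effect | Error | Percentage, no baseline | Percentage + baseline | Follow-up + baseline |
|---|---|---|---|---|---|
| A, mean 15, correlation 0.6 | additive | additive | – | 38% | 69% |
| B, mean 18, slope 0.7 | additive | additive | 59% | 67% | 78% |
| B, mean 18, slope 0.7 | proportional | additive | 56% | 61% | 80% |
| A, mean 15, correlation 0.8 | additive | proportional | – | 95% | 88% |
| B, mean 18, slope 1 | additive | proportional | 84% | 84% | 70% |
| A, mean 15, correlation 0.6 | proportional | proportional | – | 48% | 62% |
| B, mean 18, slope 0.5 | proportional | proportional | 48% | 63% | 64% |

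With additive error, follow-up adjusted for baseline had more power in every scenario run. With proportional error, either model can win. HAMIS and HAQ-DI were not simulated.

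**The case against.** Five points can be made for the plan as it stands.

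- **The main comparison does not use percentages.** This stands. A reader might infer that the primary grip result is compromised. It is not, because the between-group test is on delta. The regressions are secondary.
- **The plan does not say that baseline or arm is left out.** This stands too. The text is silent, so omission cannot be asserted. The marker rates of 24-67% apply if baseline is omitted, and the power figures apply only if arm is included.
- **Percentage change is not always less precise.** A reader might infer that it loses unless effect and error are both proportional to baseline. The figures contradict that in both directions: it wins with an additive effect and proportional error (95% against 88%; 84% against 70%) and can lose with both proportional (48% against 62%). What matters most is whether error grows with baseline and, when baseline is omitted, how strong regression to the mean is.
- **Zero baselines are not shown to occur.** Correct. The documents give neither score ranges nor baseline distributions. However, the eligibility criteria set no minimum disability and exclude serious contracture, so mild hands can enter and a rule is needed.
- **Adjusting for baseline does not cure the marker problem.** Correct. For a marker of true status the adjusted model flags more often than the plan's outcome (30-52% against 4-20%), and severity indices may well be of that kind. This limits what any of these models can say about predictors. It is not a reason to keep the ratio.

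**Conclusion.** The point holds in limited form. That the ratio is undefined at a zero baseline, with no rule given, follows from the formula alone. That an inert marker of the observed baseline can be flagged far above 5% is shown for grip, at about 24-67% without baseline in the model. This depends on assumed means and correlations and on regression to the mean; without the latter the rate is 5-9%. Loss of precision for arm is usual when error does not grow with baseline, or when baseline is omitted and regression to the mean is marked. It is not general, and it matters only if arm is in the model. No between-group conclusion on delta changes. This is a worthwhile, inexpensive correction to secondary analyses, held with medium confidence because the baseline distributions are not in the documents.

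**What to change.** In the four regressions, use the follow-up score as the outcome, at one named assessment that is also the one used for delta. Keep the baseline score and arm in every model, and list the candidate predictors. Report an absolute-change model with arm as a sensitivity analysis, and say where the two disagree: baseline adjustment over-flags markers of true status, absolute change over-flags markers of the observed baseline. Arm is randomised and so free of this problem; describe every other predictor result as an exploratory association. Keep percentage change as a description only, with a stated rule for a zero baseline.

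The cost is some wording, four re-fitted models and four sensitivity fits, all from data already collected. The downsides are that results are no longer in percentages and that some power for arm may be lost if error is proportional to baseline. In the grip scenarios above, that loss is 95 − 88 = 7 points in set-up A and 84 − 70 = 14 points in set-up B with no regression to the mean.
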